1 BACKGROUND

1.1 Disease Review

Hepatitis B virus (HBV) is a complex, small deoxyribonucleic acid (DNA) virus that goes through a ribonucleic acid (RNA) intermediate life cycle requiring reverse transcription. After transmission through infected blood, contaminated body fluids or through perinatal transfer, the virus infects the liver and can then either integrate into the hepatocyte genome or can exist as a stable chromosomal closed circular DNA. Once infection takes place, HBV infection results in chronic liver disease in 5-10% of infected adults, whereas the rate for perinatal transmission is the opposite, with greater than 90% of infected neonates progressing to chronic disease [1]. After a chronic HBV (CHB) infection is established, the rate of natural clearance is minimal. Such CHB infection frequently progresses to necrotic inflammation and ongoing liver damage, which may lead to cirrhosis and hepatocellular carcinoma (HCC) [1].

1.2 Treatment Review

Highly effective prophylactic vaccines were implemented in the early 1980's; however, these vaccines are ineffective once infection is established [2]. Despite the wide use of prophylactic vaccines, there are an estimated 240 million CHB carriers and over 686,000 related deaths per year worldwide [3].

Two classes of antiviral therapies have been approved and recommended for treatment of hepatitis B: interferons (IFNs) and nucleotide analogues (NAs). The use of IFN results in higher rates of hepatitis B e-antigen (HBeAg) and hepatitis B surface antigen (HBsAg) loss compared to NAs.

Pegylated IFN administered for up to 52 weeks results in HBsAg loss in 3-7% of patients compared to 0-3% HBsAg loss after the same duration of NA therapy. Response to IFN is also more durable, and HBsAg loss may occur after cessation of treatment, while virological relapse is frequent after cessation of NA. However, IFN is less effective at suppressing viral replication compared to NAs, requires parenteral administration, is associated with significant side effects, and is contraindicated in patients with decompensated cirrhosis or severe exacerbations of hepatitis and those with autoimmune or psychiatric illnesses.

Nucleotide analogues are administered orally and have negligible adverse effects. The recommended first-line NAs, entecavir and tenofovir, have low risk of drug resistance; but the requirement for indefinite therapy increases the cost and the risk of non-adherence.[4]

Various combinations of IFN and NA have been evaluated, but most studies have not shown an added benefit compared to monotherapy [5,6,7]. A recent study showed that combination of pegylated IFN and tenofovir increased the rate of HBsAg loss to 9.1% at Week 72, but the benefit was mainly observed with those infected with HBV genotype A [8].

Many research programs are ongoing to develop new treatment concepts that focus on the clearance of HBsAg in a significant proportion of patients, with the principle aims of: 1) stopping treatment with no risk of virological relapse and no risk of liver disease progression and, 2) to further decrease the risk of HCC. Several potential target mechanisms for immune modulation to restore HBV specific immune responses in conjunction with profound inhibition of HBV replication and HBsAg production to attain immunological control are being evaluated [3].

The immune clearance of CHB is likely to depend on the use of modalities that induce effective CD8+ T cells [9,10]. For over two decades vaccination strategies to induce these CD8+ T cells

to counter such infections as tuberculosis (TB), human immunodeficiency virus (HIV) and malaria have been investigated [11,12,13]. One platform approach that has induced remarkably high levels of T cells in man has been to use a non-replicating adenovirus "prime" followed by a heterologous viral vector "boost" utilising a non-replicating pox virus (modified vaccinia Ankara [MVA]) [14,15,16]. Non-replicating chimpanzee adenoviruses are often used rather than human adenoviruses, as there is minimal prior immunity to the vector itself. [17,18] The combination of chimpanzee adenoviruses (used in thousands of participants) plus MVA (administered to over 130,000 people) has been shown to induce large immune responses in man in malaria, TB, HIV, influenza and respiratory syncytial virus [13,16,19-22]. The chimpanzee adenovirus vector proposed in this study (chimpanzee adenovirus Oxford 1; ChAdOx1), a serogroup E adenovirus, has been administered to over 200 people in trials of Middle East Respiratory Syndrome (MERS), influenza, TB, chikungunya, and prostate cancer, and has been safe and immunogenic. It has also been modified to enhance immunogenicity through the addition of a short shark invariant chain (S1I) sequence and use of the tissue plasminogen promoter.

Hepatitis B virus circulates in the world as a number of genotypes (A-I), of which the most prevalent (especially in Asia) is genotype C [23]. The proteins expressed by ChAdOx1 in this study include most of the HBV genome from a genotype C consensus, including HBsAg, polymerase and core. In vitro experiments have demonstrated that the HBV polymerase was successfully inactivated through the insertion of point mutations at critical sites. In order to stop aggregation of surface antigen, the protein was split into two separate coding regions in the viral vectors.

The genetic HBV insert was then cloned into both the ChAdOx1 vector (chimpanzee adenovirus vectored hepatitis B virus vaccine; ChAdOx1-HBV), and also into an MVA vector (MVA-HBV) that will be used as a boost in a subsequent study after the evaluation of the ChAdOx1-HBV given alone is completed.

This study is designed to assess the safety and immunogenicity of ChAdOx1-HBV and to assess the breadth of responses to the proteins encoded by the vaccine vector. The cross reactivity to other genotypes will also be assessed. Doses of ChAdOx1 vaccines in previous studies have varied from 10^8 to over 10^{11} viral particles (vp) per dose and the middle two doses will be evaluated in this study to prepare for a further heterologous prime-boost regimen.

1.3 Summary of Non-clinical Studies

Immunogen design: 1,447 HBV genotype C nucleotide sequences (HBV database) were aligned, and an HBV genotype C consensus sequence was generated. Then, a patient's HBV genotype C sequence (accession number: KP017269.1 HBV isolate JP-02) that had maximum similarity to the consensus was chosen for use in the HBV immunogen design. The HBV immunogen encompasses three full length HBV-antigens (pre-core/core, polymerase and preS1/preS2/surface) along with truncated S1I and tissue plasminogen activator genetic adjuvants and it is encoded in the chimpanzee adenoviral vector. Point mutations were introduced within the polymerase protein encoded in the immunogen in order to abolish its function and to ensure no replication-competent HBV genome could arise from the immunogen sequences. An HBV-polymerase assay performed by the laboratory of [name] at University Hospital Freiburg, Germany, confirmed the absence of polymerase activity of the polymerase contained in the HBV immunogen. A schematic of the HBV immunogen is shown in [Figure 1](#).

Figure 1 Schematic of Hepatitis B Virus Immunogen

The HBV immunogen was cloned and recovered into the ChAdOx1 vector genome to generate ChAdOx1-HBV. Research stocks of the ChAdOx1-HBV vector were generated at the viral vector core facility of the Jenner Institute, University of Oxford.

Preclinical immunogenicity testing: ChAdOx1-HBV was found to be highly immunogenic when tested in mouse immunogenicity experiments in both inbred (BALB/c, C57BL/6) and outbred (CD-1) mice, measured using interferon-gamma (IFN- γ) enzyme-linked immunospot (ELISpot) and intracellular cytokine staining (ICS) assays.

A Good Laboratory Practice toxicology study is ongoing (see Investigator's Brochure for further study details and results).

1.4 Summary of Clinical Experience

ChAdOx1 has been administered to over 200 participants (MERS, malaria, influenza and prostate cancer) and as the prime for an MVA boost in the malaria, influenza and prostate cancer studies (NCT03399578, NCT03203421, NCT01818362, NCT01623518 and NCT03815942). In all of those studies, extremely high levels of transgene-specific CD4+ and CD8+ T cells have been induced and there have been no vaccine-associated serious adverse events (SAEs). This is the first clinical study for the HBV ChAdOx1 vaccine.

Further information on ChAdOx1-HBV is contained in the Investigator's Brochure; this information should be reviewed prior to study initiation.

1.5 Study Rationale

Chronic hepatitis B virus infection is a global public health challenge on the same scale as TB, HIV and malaria. The current prophylactic vaccine has no effect on established chronic infection. Available treatments suppress viral replication, but they are not curative, largely due to the persistence of the viral covalently closed circular DNA (cccDNA) transcriptional template in infected hepatocytes and the failure of chronically infected patients to mount an immune response that is sufficiently robust, functional, and sustained to clear the infection. Thus, in most cases, treatment must continue for life. However, even successfully virally suppressed patients may still develop liver cancer.

Many research programs are ongoing to develop new treatment concepts that focus on the clearance of HBsAg in a significant proportion of patients, with the principle aims of: 1) stopping treatment with no risk of relapse and no risk of liver disease progression and 2) to further decrease the risk of HCC.

Pre-clinical models still have considerable limitations in this indication, and important gaps in our understanding of the HBV replication cycle and the host immune response must be addressed to expand the exploitable vulnerabilities in the replication cycle that can be targeted therapeutically to cure the infection.

A major effort has been made to compare the efficient integrated response resulting in HBV clearance of acute infection to the dysregulated response observed in patients with chronic hepatitis B. A complex interplay of innate and adaptive immune responses is essential for viral clearance and a failure of these responses can result in liver pathogenesis. CD8+ T cells are the main effector cells that eliminate the virus by cytolytic and non-cytolytic effector functions

[24,25]. Sufficient CD4 T cell activity and the production of neutralising anti-HBV envelope antibodies are required for protective immunity [26].

The combination of chimpanzee adenoviruses (used in thousands of participants) plus MVA (administered to over 130,000 people) has been shown to induce large immune responses in man in malaria, TB, HIV, influenza and respiratory syncytial virus [13,16,19-22].

Doses of ChAdOx1 vaccines in previous studies have varied from 10^8 to over 10^{11} vp per dose and the middle two doses will be evaluated in this study to prepare for a further heterologous prime-boost regimen. The safety of ChAdOx1-HBV and the breadth of systemic and liver-specific immune responses will be explored. A prime-boost strategy using ChAdOx1 vector (ChAdOx1-HBV) and an MVA vector (MVA-HBV), with and without anti-programmed cell death protein 1 (PD-1) will be evaluated in a subsequent study.

1.5.1 *Rationale for Investigation of Dosing Interval With Respect to COVID-19 Vaccines*

There are concerns that the prior use of a vectored vaccine may result in anti-vector responses, which would decrease the response to a subsequent use of the same vector. Specifically, there have been concerns raised that the use of the AstraZeneca ChAdOx1-SARS-CoV-2 vaccine (AZD1222 or Vaxzevria®) might reduce either the antibody or T cell response to a subsequent vaccine using the same vector. This potential decrease has been attributed to the induction of a neutralising cross-reactive T cell response to the viral vector.

For adenoviral vectors, prior infection with a replicating adenovirus of the same strain (e.g., human adenoviral 5) does appear to have an effect on the subsequent T cell and antibody response. However, this neutralisation is primarily directed against the fibre protein. This interference was a primary motivating factor in the development of replication-incompetent adenoviral vectors based on simian strains (chimpanzee, bonobo, and gorilla). In contrast, the neutralisation resulting from the use of the replication incompetent adenoviral vectors themselves is directed primarily to the abundant hexon capsid protein, and this response may have only minor effect on cell entry and immunogenicity, mainly mediated by the fibre.

In studies of AZD1222, there was no statistical relation between the level of neutralisation response following the first immunisation, and the resultant antibody or T cell response (as measured by IFN- γ ELISpot) following a second immunisation [27]. Likewise prior receipt of a ChAdOx1 vaccine (either ChAdOx1-MERs or ChAdOx1-mening) had no effect on the response to AZD1222.

However, the improvement of antigen-specific immunogenicity of a delayed interval is supported by reports in the literature of clinical trials assessing homologous or heterologous prime-boost regimes with adenoviral vectors [28-33]. In summary, the longer the interval between first and second dose of the adenoviral vector, the better the antigen-specific boosting capacity of the second dose. This has been mostly studied with antibody responses to the same adenoviral vector encoding the same antigen. This has been in part attributed to declining titres of vector-neutralising and vector-binding antibodies with time. Specifically, antigen-specific antibodies were boosted 3-fold when the boosting interval was 4 weeks, but this increased to 10-fold when the interval between the two vaccines was 24 weeks [29]. In another study, antibody titres were boosted 10-fold after a prime-boost interval of 12 weeks, and T cells were also boosted [28]. Nonetheless, it is well-known that increasing interval may boost responses, and the association of the increase in titres with increasing intervals has not been clearly shown in any of the cited studies to be attributed to the level of anti-vector neutralizing antibodies.

It is important to note that all previous clinical experience with second administration of the same adenoviral vector has been in the context of a single antigen, for example, Ad26-gag prime followed by Ad26-gag boost. This is in contrast to the scenario discussed here, where a possible administration of the ChAdOx1-nCoV-19 vaccine is followed by administration of a ChAdOx1 vector encoding HBV antigens. This is not a prime-boost scenario per se but rather the re-use of the same vector platform in a different indication.

Given this uncertainty and the improved responses seen three months after initial immunization compared to one month in studies of homologous prime-boost of the same antigen, and lacking clear data, the Sponsor has advised that participants not receive the ChAdOx1 vaccine in this and other [REDACTED]-sponsored trials until at least three months after receiving the AZD1222 or J&J hAd26, and that a three-month interval should also be advised if the COVID-19 vaccine follow entry into our study. However, this is not based on firm data, and either a shorter or longer interval may indeed be warranted.

To support this interval, this study aims to produce data of the response in healthy volunteers to our ChAdOx-1 HBV vaccine following the use of the AZD1222 vaccine. T cell responses (the critical immunological factor in chronic HBV infection) will be compared in participants who have received either a prior two-dose series of AZD1222 with those who have received at least two prior doses of either the Pfizer mRNA COVID 19 vaccine (Comirnaty) or the Moderna COVID-19 vaccine (Spikevax). Due to the recommendation to use the AZD1222 in those over the age of 40 years, we will confine our study to 40-60 years of age and keep the interval from the latest COVID-19 vaccine to a narrow window of 10-18 weeks. No interference on HBV -focused T cell responses is expected from either the Pfizer vaccine or the Moderna vaccine, so the interval from the latest COVID-19 vaccine will be between 6 to 30 weeks

2

STUDY OBJECTIVES AND ENDPOINTS

Objectives	Endpoints
Primary	Primary
Determine the safety and tolerability of different doses of a single vaccination of ChAdOx1-HBV in healthy participants and in participants with CHB infection and virally suppressed with oral antiviral medication.	Incidence of safety and reactogenicity events: 
 • Adverse events and/or adverse events leading to study discontinuation • Serious adverse events • Grade ≥ 3 local and systemic reactions
Secondary	Secondary

 • Determine the immunogenicity of ChAdOx1-HBV in (A) healthy participants and in (B) participants with CHB, virally suppressed with oral antiviral medication 
Determine the effect of ChAdOx1-HBV on the level of HBsAg in participants with CHB infection, virally suppressed with oral antiviral medication
	
 • A multi-parameter index made of CD4+ magnitude, CD4+ avidity, and CD8+ magnitude • Mean reduction in HbsAg titre at Day 84 and Day 168 post-vaccination (last visit) • Proportion of CHB participants with HbeAg and HbsAg loss • Proportion of CHB participants with HbeAg and HbsAg seroconversion • Reduction of hepatitis B DNA levels • Total T cell response to the antigens encoded by ChAdOx1-HBV as measured in a peptide-stimulated ELISpot assay
Exploratory	Exploratory
Determine the effect of ChAdOx1-HBV on virological and immunological systemic and intrahepatic changes in participants with CHB infection and virally suppressed with oral antiviral medication.	
 • Effect on serum hepatitis B core-related antigen (HBcAg) • Effect on serum hepatitis B circulating pre-genomic ribonucleic acid (pgRNA) • Liver fine needle aspirate (LFNA) assays will be used to quantify and characterise intrahepatic immune and parenchymal cells and/or HBV DNA and RNA transcripts • Effect of prior AZD1222 on the CD4+ and CD8+ T cell magnitude and phenotype as measured by multiparameter flow cytometry

[figure not shown]

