4.2 Inclusion Criteria

Participants must meet *all* the following criteria to be eligible for the study:

1. Adult males or females aged ≥ 18 to ≤ 65 years at screening
2. Body Mass Index $\leq 30 \text{ kg/m}^2$
3. Able to provide informed consent indicating they understand the purpose of, and procedures required, for the study and are willing to participate
4. If female, willing not to become pregnant up to 8 weeks after last dose of study vaccine, not breast feeding
5. If female: Not pregnant and one of the following:
 - Of non-childbearing potential (i.e. women who have had a hysterectomy or tubal ligation or are post-menopausal, as defined by no menses in ≥ 1 year)
 - Sexual abstinence, only if the participant refrains from heterosexual intercourse during the entire study period and it is the usual lifestyle of the participant
 - Of childbearing potential but agrees to practice highly effective contraception for 4 weeks prior to study vaccine and 8 weeks after study vaccine. Highly effective methods of contraception include one or more of the following:
 - Male partner who is sterile (medically effective vasectomy) prior to the female participant's entry into the study and is the sole sexual partner for the female participant
 - Combined (estrogen and progestogen containing) hormonal contraception associated with inhibition of ovulation:
 - oral
 - intravaginal

- transdermal
- Progestogen-only hormonal contraception associated with inhibition of ovulation:
 - oral
 - injectable
 - implantable
 - An intrauterine device
 - Bilateral tubal occlusion

Healthy participants (cohorts 1 and 2):

6. Considered to be healthy with no current conditions that may significantly impair participant safety or influence study results, in the opinion of the Investigator

Participants with well controlled CHB (cohorts 3 and 4):

7. Documented evidence of chronic HBV infection (e.g. HBsAg positive ≥ 6 months with detectable HBsAg levels at screening)
8. Receipt of only either entecavir or tenofovir for at least 12 months before screening
9. Virally suppressed (HBV DNA <40 IU/mL for ≥ 6 months)
10. HBsAg <10000 IU/mL

Healthy participants (cohort 5):

11. Considered to be healthy with no current conditions that may significantly impair participant safety or influence study results, in the opinion of the Investigator
12. Adult males or females aged ≥ 40 to ≤ 60 years at screening
13. Completed second dose of COVID-19 AZD1222 vaccine 10 to 18 weeks before enrolment

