4.3 Exclusion Criteria

1. Presence of any significant acute or chronic, uncontrolled medical/psychiatric illness
2. Hepatitis C virus (HCV) antibody positive.
3. HIV antibody positive
4. History or evidence of autoimmune disease or known immunodeficiency of any cause
5. Prolonged therapy with immunomodulators (e.g. corticosteroids) or biologics (e.g. monoclonal antibodies, IFN) within 3 months of screening
6. Receipt of immunoglobulin or other blood products within 3 months prior to screening
7. Receipt of any investigational drug or vaccine within 3 months prior to screening
8. Cohorts 1-4: Receipt of any adenoviral vaccine within 3 months prior to administration of ChAdOx1-HBV on Day 0, or plan to receive an adenoviral-based vaccine within 3 months after Day 0

Cohorts 5 and 6: Receipt of any adenoviral vaccine (other than AZD1222 per inclusion criterion 13) within 3 months prior to administration of ChAdOx1-HBV on Day 0, or plan to receive an adenoviral-based vaccine within 3 months after Day 0

9. Receipt of any live vaccines within 30 days prior to screening
10. Receipt of any inactivated vaccines within 14 days prior to screening
11. History of allergic disease or reactions likely to be exacerbated by any component of the vaccine
12. Any history of anaphylaxis in reaction to vaccination
13. Malignancy within 5 years prior to screening with the exception of specific cancers that are cured by surgical resection (e.g. except basal cell skin carcinoma of the skin and cervical carcinoma). Participants under evaluation for possible malignancy are not eligible
14. Current alcohol or substance abuse judged by the Investigator to potentially interfere with participant safety and compliance
15. Significant cardiac disease or unstable uncontrolled cardiac disease
16. Any laboratory test at screening which is abnormal and which is deemed by the Investigator to be clinically significant
17. Any other finding that, in the opinion of the Investigator, deems the participant unsuitable for the study

Additionally, for healthy participants (cohorts 1, 2, 5 and 6)

18. HBsAg positive

Additionally, for participants with well controlled CHB (cohorts 3 and 4)

19. Co-infection with hepatitis delta
20. Documented cirrhosis or advanced fibrosis indicated by a liver biopsy within 6 months prior to screening.

In the absence of an appropriate liver biopsy, either 1 of the following:

- Screening Fibroscan with a result >9 kPa within ≤ 6 months of screening or

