10 STATISTICAL CONSIDERATIONS AND ANALYSIS PLAN

10.1 Sample Size Determination

No formal sample size calculation for cohorts 1 to 4 was performed and sample size is based upon feasibility considerations. The chosen number of participants is considered sufficient to meet the objectives for the study.

The sample size for cohorts 5 and 6 is based on the ELISpot results of ChAdOx1-HBV administered to healthy adults at a dose of 2.5×10^{10} which resulted in a mean of 1,000 +/-500 spot forming units in three adults who had samples examined by same day analysis at Oxford University. Assuming the same response in 15 volunteers in each cohort, the sample size is powered to detect a 45% decrease in the T cell response in the participants receiving prior AZD1222 compared to the Pfizer/Moderna mRNA COVID-19 vaccine.

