10.1.8. Examination of Subgroups

Due to the small number of participants enrolled in this study, no subgroup analysis will be performed.

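### Cohorts 5 and 6 are meant to support a three-month interval after AZD1222, but one pooled 10-18 week window with no between-cohort estimate cannot do that, and seeing no decrease would not exclude a loss of about a third

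*Protocol*

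**What the plan says.** Protocol 1.5.1 records the sponsor's advice that participants should not receive the study vaccine "until at least three months after receiving the AZD1222 or J&J hAd26". It then qualifies the advice: "However, this is not based on firm data, and either a shorter or longer interval may indeed be warranted". The next paragraph gives the reason for the two added cohorts: "To support this interval, this study aims to produce data of the response in healthy volunteers to our ChAdOx-1 HBV vaccine".

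The cohort that carries this purpose is defined by inclusion criterion 13 (Protocol 4.2): "Completed second dose of COVID-19 AZD1222 vaccine 10 to 18 weeks before enrolment". The matching exclusion criterion (Protocol 4.3) is written so that it does not remove these people: "Receipt of any adenoviral vaccine (other than AZD1222 per inclusion criterion 13) within 3 months prior to administration of ChAdOx1-HBV on Day 0". The secondary objective (Protocol synopsis; SAP 5.2) is narrower than 1.5.1. It asks whether prior AZD1222 lowers T cell responses when given 10-18 weeks before ChAdOx1-HBV, and does not mention three months.

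On size, Protocol 10.1 and SAP 8 state that "the sample size is powered to detect a 45% decrease in the T cell response", comparing cohort 5 with cohort 6. On analysis, SAP 10.1.3 plans no formal statistics and SAP 10.7.2 summarises ELISpot results by treatment group and antigen. SAP 10.1.8 adds that, because numbers are small, "no subgroup analysis will be performed". COVID-19 vaccination dates appear in Listing 16.2.12 and nowhere else in the planned outputs.

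**The concern.** Supporting a waiting period means showing that little response is lost once the wait is over. That needs two things: results that can be tied to the interval in question, and enough precision to rule out a loss that would matter. The plan provides neither. The window is pooled across three months, no output relates response to the time since AZD1222, and the cohorts are sized to detect a decrease. Neither document gives a margin, an interval estimate for the difference, or a statement of what result would count as support.

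If cohort 5 responds less than cohort 6, the planned tables cannot show whether the shortfall sits below or above three months. If the two look alike, the rationale in 1.5.1 invites the reader to take that as support, although the data could be compatible with losing about a third of the response.

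**Working it through.** **Inputs.** Mean 1,000 SFU, spread +/-500, three adults, 15 per cohort (Protocol 10.1; SAP 8). The +/-500 is not labelled, and I read it as an SD. Those sections state no alpha, sidedness or power, so I show both one- and two-sided 5%.

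**Standard error of the difference.** 500 x sqrt(2/15) = 182.6 SFU.

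**The plan's own 45%.** Detectable difference at 80% power, normal approximation:
- one-sided 5%: (1.645 + 0.842) x 182.6 = 454 SFU, or 45%, which reproduces the stated figure;
- two-sided 5%: (1.960 + 0.842) x 182.6 = 511 SFU, or 51%, which does not.

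The stated figure is therefore consistent with a one-sided 5% calculation at about 80% power.

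**What equal observed means would leave open (t, 28 df).**
- One-sided 5% bound: 1.701 x 182.6 = 311 SFU, or 31% of 1,000.
- Two-sided 95% interval: 2.048 x 182.6 = 374 SFU, or 37% of 1,000.

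**Sensitivity to the assumptions.**

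| Assumption | Loss compatible with equal means (two-sided 95%) |
|---|---|
| SD 300 | 22% |
| SD 400 | 30% |
| SD 500 | 37% |
| SD 600 | 45% |
| SD 750 | 56% |
| +/-500 is a standard error (SD = 500 x sqrt(3) = 866) | 65% |
| Log scale, CV 0.5 | 30% (25% with a one-sided 5% bound) |

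An SD of 500 from three people has a 95% confidence interval of roughly 260 to 3,140, so all these figures are indicative.

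**The interval.** Three months is 365.25/4/7 = 13.0 weeks, so a 10-18 week window holds time on both sides of it. The passages also use different clocks. Criterion 13 counts to enrolment, and Protocol 4.1 glosses enrolled as having consented. Screening may run from Day -42, which is 6 weeks. On that reading someone who consents at 18 weeks could be dosed at up to 18 + 6 = 24 weeks, whereas the secondary objective counts 10-18 weeks to ChAdOx1-HBV itself.

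**Could a subset rescue it?** As an illustration only, if 10 of the 15 were dosed at or beyond 13 weeks, their comparison with 15 in cohort 6 would have a two-sided 95% half-width of 2.069 x 500 x sqrt(1/10 + 1/15) = 422 SFU, or 42%. That is wider than the pooled comparison.

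**The case against.** Several points on the other side are sound.

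- **Entry from 10 weeks looks deliberate.** Section 1.5.1 allows that a shorter or longer interval may be right, and a window around three months fits that and the secondary objective. This stands: the documents do not show the lower limit to be a mistake. But such a window informs the choice of interval only if response is looked at against interval, and no output does so.
- **Including people below three months could be conservative.** Protocol 3.3 says interference fades with time, so earlier recipients should make it easier to see. This stands in part. The same premise means that people at the long end of the window dilute any loss around three months, and the argument helps only once an important loss has been excluded.
- **No decision rule exists.** A reader might infer that the sponsor would declare the interval supported if no decrease appears. No document says so, and 1.5.1 speaks of producing data. The fair criticism is that nothing guards against that reading.
- **The number below 13 weeks is unknown.** A reader might take 3/8 of 15, about 6 people. That treats enrolment as Day 0 and assumes even entry. Time spent in screening would lower the count at dosing, and the documents do not support any particular figure.
- **37% depends on the framework.** This stands. The objective is directional, and the one-sided bound gives 31%.
- **Fifteen people are too few for analysis by interval.** This also stands, and SAP 10.1.8 gives small numbers as its reason. It limits the remedy to a descriptive plot.

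It is also tempting to turn the 45% into an exclusion margin. It is a detectable-effect figure with no stated justification as a margin. Since 450 - 374 = 76 SFU, that rule would count as support not only equal means but also an observed loss of about 7%, while losses well over a third remained compatible with the data.

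**Conclusion.** The concern holds in a limited form. The rationale in 1.5.1 claims more than the design and planned outputs can give. They can describe responses after AZD1222 across a 10-18 week window, but cannot support three months as such. A finding of no decrease would leave open a loss of about 31% (one-sided 5% bound) to 37% (two-sided 95% interval).

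Those figures assume equal observed means, 15 evaluable per cohort and an SD of 500 drawn from three adults. A log-scale analysis or a smaller SD gives less, and a larger SD gives more. The secondary objective is already correctly worded, so the fault lies in the stated rationale and in the missing estimate. It does not lie in the choice of window.

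**What to change.** 1. **Protocol 1.5.1.** State the aim, and later the conclusion, as the secondary objective does: the effect of AZD1222 given 10-18 weeks before ChAdOx1-HBV. Do not present it as support for three months. Reconcile the three-month advice, the window counted to enrolment, and the objective counted to ChAdOx1-HBV.
2. **SAP 10.7.2.** Report the cohort 5 versus cohort 6 ELISpot difference or ratio with its confidence interval, naming in advance the visit and the response used, since the shell of Table 14.2.4 repeats over visits and antigens. State the largest loss compatible with the data, and say that the absence of a clear decrease will not be read as support for the interval.
3. **One figure.** Plot each cohort 5 response against actual weeks from the second AZD1222 dose to Day 0, with 13 weeks marked, using the dates in Listing 16.2.12 and the study vaccination date. Label it descriptive, because 15 participants cannot separate intervals.

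The cost is a less favourable stated aim, one estimate and one plot. No extra participants, visits or samples are needed.
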